## 9.7.6 Analysis for Objectives of HCPs' Utilization of the aRMM Tools

The following will be summarized using the Completed Surveys analysis set:

- The proportion distributing the Guide to Patients/Carers prior to treatment decision.
- The proportion distributing the Patient Card prior to treatment decision.

### 9.8 Quality Control

treatment with Casgevy.

Data will be collected using a secure and validated online EDC system. The Information Technology applications are governed by a development approach to ensure compliance to international regulations and guidance: US FDA (Guidance for Industry: Computerized Systems Used in Clinical Trials and Code of Federal Regulations Title 21 Part 11), European Commission (EudraLex Annex 11: Computerised Systems), EMA (e.g., EU Good Pharmacovigilance Practices [GVP]) and International Council for Harmonisation (ICH). The system is compliant for the entry, storage, handling, analysis, and transmission of electronic information.

Respondent-identifying information will be stored separately from the survey responses.

The EDC system will be set up such that HCPs who do not answer screening questions or who provide responses indicating ineligibility will be automatically unable to complete the survey. These ineligible HCPs will be provided with a message thanking them for their time and explaining their ineligibility to participate.

#### 9.9 Limitations of the Research Methods

Participants will be self-selected since they will voluntarily respond to the invitation to participate, so those who choose to respond to the survey may differ in their understanding of

the important safety information from those who elect not to participate. This is a common limitation of all studies that rely on voluntary participation.

It is also possible that the respondents have an acceptable understanding of the important safety information despite not using the Guide for HCPs. The survey can assess the HCPs' understanding of the important safety information but cannot clearly determine if their knowledge is a result of reading the Guide for HCPs.

All data from the survey are self-reported and therefore susceptible to possible reporting bias. An HCP may know and report the desired behavior even if they do not undertake such behavior to provide a socially desirable response.

There is also the possibility that the email invitation may be blocked or marked as spam in the HCPs' email. This can be mitigated by field staff (Medical Scientific Liaisons [MSLs]) personally discussing this study with relevant HCPs during encounters.

As TDT and SCD are rare diseases and Casgevy is a novel therapy, the number of centers treating patients with Casgevy, the number of patients eligible for Casgevy treatment, and the number of HCPs counseling eligible patients is likely to be small. To increase response rates to the survey invitation, the MSLs will emphasize the importance of the survey as part of a regulatory commitment during encounters with relevant HCPs.

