## 9.2 Setting

Data collection via a web-based survey will be initiated in all countries in the EU where Casgevy is launched approximately 18 months after first drug availability has been achieved in any EU country.

The Guide for HCPs, the Guide for Patients/Carers and the Patient Card are provided to HCPs who are trained on the use of Casgevy at authorized treatment centers (ATCs) in each country in accordance with local distribution/communication plans as agreed by National Competent Authorities (NCAs). As both TDT and SCD are rare diseases and Casgevy is a new novel therapy, there are a limited number of HCPs per country who counsel eligible patients.

The target population will be all HCPs who have counseled patients regarding Casgevy as a treatment option across all ATCs in all EU countries where Casgevy is launched. The same survey will be used for all participating countries to ensure consistency in testing the target population. As such, variability of survey results based on geography is not anticipated.

In the event that the target number of completed surveys is not obtained after the survey has been implemented and should additional ATCs be activated, the Marketing Authorization Holder (MAH) will extend the survey, in order to reach the target number of completed surveys.

The survey will be administered via the internet, which will allow respondents to participate at a time and location that is convenient for them.

Eligible HCPs who respond to the survey invitation will make up the study population. Survey invitations will be sent to all potentially eligible HCPs at all ATCs in the EU where Casgevy is launched, with the expectation to obtain approximately 30 completed responses (see Section 9.5 Study Size).

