#### 9.4 Data Sources

The data source will be surveys completed by HCPs who have counseled patients regarding Casgevy as a treatment option at ATCs.

The HCPs will receive an invitation letter to participate in the survey. The invitation letter (APPENDIX 1.2) will include: an overview of the rationale for the survey, information on how to access the survey online and a unique invitation code to ensure that the invitation is used only once. Based on survey uptake, reminder notices will be sent to those who have been invited but have not yet participated. Participating HCPs' identifying information will be collected for the purposes of providing financial compensation based on Fair Market Value, as allowed by local laws and country regulations and to comply with laws and regulations regarding notification of payments made on behalf of a pharmaceutical company.

A structured, self-administered questionnaire will be used to collect survey data (APPENDIX 1.1). It is comprised of closed-ended questions and statements with multiple response choices.

User testing will be performed prior to finalization of the questionnaire. The user testing procedure is designed to assess comprehension among HCPs regarding the words and phrases used in survey questions and response options. User testing will also assess the clarity of the survey questions as presented to the HCPs and the flow and ease of completing the survey. Findings and recommendations from the user testing will be incorporated into the survey.

The survey will be voluntary. The collection of any personal, identifying information (e.g., first name, last name, address) from respondents will only be used for processing of HCPs' financial compensation, as stated above and will be stored in a separate database.

Each individual will be randomly assigned a unique code to access the survey. Each unique code will be deactivated upon use to prevent the code from being used to complete the survey multiple times. Individuals will not have to actively "decline to complete the survey." Participants who agree to respond to the survey will begin with a screening module with questions to confirm eligibility.

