#### 9.5 Study Size

The target sample size is approximately 30 completed surveys. Invitations will be sent to all potentially eligible HCPs at all ATCs in the EU where Casgevy is launched, with the expectation to obtain approximately 30 completed surveys. The study size is not based on statistical considerations but has been determined by considering the rarity of SCD and TDT and the small number of HCPs who will counsel patients regarding use of Casgevy as a treatment option. Depending upon the country population and healthcare organization, it is estimated that there will typically be fewer than 10 centers per country that will treat patients with Casgevy. Thus, the potential pool of HCPs eligible to participate in the survey is small.

While it is generally accepted that uptake to invitations for survey participation is generally low, it is anticipated that the response rate to the Casgevy survey will be higher for the following reasons: the MAH has well-established relationships with the potential participants and field medical liaisons are in regular face-to-face contact with potential participants and these contacts will be used to encourage participation. However, as stated in Section 9.2 above, survey invitations will be extended in time if the target of 30 completed surveys is not reached, should additional ATCs be activated. Estimated precision based upon a sample size of 30 is set out in Table 1 below.

 Table 1
 Estimated Precision, by Sample Size and Proportion

	Proportion of Correct Responses Observed	Precision a	
Sample Size	(%)	Low (%)	High (%)
	20	7.7	38.6
30	40	22.7	59.4
	60	40.6	77.3
	80	61.4	92.3
	90	73.5	97.9
	100	88.4	100.0

<sup>a 95% confidence interval, 2-sided (Clopper-Pearson 1934 method).

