#### 9.9.1 Controls to Minimize Bias

A number of controls will be in place to ensure that the survey is conducted to minimize bias, including the following:

- Knowledge questions will be randomized and presented individually to minimize the potential for positional bias.
- HCPs cannot skip ahead or go back to a question once the question has been answered. All questions presented must be answered in order to complete the survey.
- HCPs will be provided with a unique code during the recruitment process in order to gain access to the internet-based systems. The code will be inactivated after use to minimize exposure bias and fraud.
- Respondent identifiers will be stored separately from survey responses thus limiting HCP concerned that their answers will be identified. This is likely to minimize the social desirability bias and improve response rates.

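### The plan describes no safeguard against looking up answers in an unsupervised knowledge survey, so the correct rate judged against 80% may be biased upward by an unknown amount

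*Protocol*

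**What the plan says.** Objective 1 (Protocol section 8) is the HCPs' understanding of the safety information in the Guide.

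- **Promotion.** Section 9.5 expects a good response because "field medical liaisons are in regular face-to-face contact with potential participants and these contacts will be used to encourage participation". Section 9.9 adds that liaisons will be "personally discussing this study with relevant HCPs during encounters" and that "the MSLs will emphasize the importance of the survey as part of a regulatory commitment during encounters with relevant HCPs".
- **Advance notice.** Under section 9.4 the invitation letter contains "an overview of the rationale for the survey, information on how to access the survey online and a unique invitation code". Reminders go to those who have not yet taken part.
- **Administration.** Section 9.4: "A structured, self-administered questionnaire will be used to collect survey data". Section 9.2: it runs over the internet, "which will allow respondents to participate at a time and location that is convenient for them".
- **Access to the answers.** Section 9.2: "The Guide for HCPs, the Guide for Patients/Carers and the Patient Card are provided to HCPs who are trained on the use of Casgevy".
- **Controls.** Section 9.9.1 lists four. The first is "Knowledge questions will be randomized and presented individually to minimize the potential for positional bias". The others are no skipping or going back, a single-use access code, and separate storage of identifiers.
- **Decision rule.** Section 9.7.4 calls the measure for a KRM successful when its correct rate reaches 80%. Section 9.5 targets about 30 completed surveys.

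**The concern.** The correct rate is read as understanding. A respondent who has notice of the survey, is told that it matters to the regulator, answers alone and works where the Guide is provided can open the Guide with the question on screen. That answer is scored the same as one given from knowledge. The expected direction is one-sided: consulting the Guide would raise the correct rate and so favour declaring the measure successful. If enough respondents did so, a KRM whose unaided rate is below 80% could be reported as a success, and nothing in the data collected would show it.

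**Working it through.** **1. What each listed control and each stated limitation covers**

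| Place | Element | Addresses look-up while answering? |
|---|---|---|
| 9.9.1 | Random order, one item at a time | No; aimed at positional bias |
| 9.9.1 | No skipping or going back | Limits previewing, not look-up of the item on screen |
| 9.9.1 | Single-use code | Limits retaking, not look-up |
| 9.9.1 | Identifiers stored apart | No; aimed at social desirability and response rate |
| 9.9 | Self-selection | No; concerns who responds |
| 9.9 | Knowledge may not come from the Guide | No; concerns where real knowledge came from |
| 9.9 | Self-report and social desirability | No; the example given is reported behaviour |
| 9.9 | Spam-blocked invitations; small numbers | No |
| 9.3, 9.7.4 | Source of safety information | No; does not separate prior knowledge from look-up during the survey |

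**2. The plan's own precision figure**

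Table 1 gives 61.4% to 92.3% for 80% observed with n = 30. The exact Clopper-Pearson limits for 24/30 are 61.4% and 92.3%, so the figure reproduces, as do the other five rows. This interval describes sampling error only and would not show a systematic upward shift.

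**3. Illustration of size (assumed inputs)**

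The documents give no unaided rate u, no aided rate a and no share s of respondents who look up. With

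observed rate = (1 − s) × u + s × a,

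and s = 30%:

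| u | a | Calculation | Expected observed rate |
|---|---|---|---|
| 75% | 98% | 0.70 × 75 + 0.30 × 98 | 81.9% |
| 70% | 98% | 0.70 × 70 + 0.30 × 98 | 78.4% |
| 60% | 98% | 0.70 × 60 + 0.30 × 98 | 71.4% |
| 75% | 90% | 0.70 × 75 + 0.30 × 90 | 79.5% |

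At s = 30% and a = 98%, the expected rate crosses 80% only if u is at least (80 − 29.4)/0.70 = 72.3%.

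The break-even share is s = (80 − u)/(a − u). With a = 98%:

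- u = 75%: 5/23 = 22%, about 7 of 30.
- u = 70%: 10/28 = 36%, about 11 of 30.
- u = 60%: 20/38 = 53%, about 16 of 30.

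**4. Chance of reaching the threshold**

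This step assumes that look-up always gives the right answer (a = 100%) and treats a KRM as one yes/no outcome per HCP, which simplifies the pooled item rate. The binomial probability of at least 24/30 is:

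| u | s = 0 | s = 20% | s = 40% |
|---|---|---|---|
| 50% | 0.1% | 1.7% | 16.0% |
| 60% | 1.7% | 11.0% | 39.6% |
| 70% | 16.0% | 39.6% | 71.2% |

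Under these assumptions the effect runs from negligible to decisive. No row can be preferred on the documents.

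**The case against.** **The controls may exist elsewhere.** Section 9.9.1 introduces its list with the word including, section 10.1 mentions survey instructions, and the questionnaire and invitation letter (Appendices 1.1 and 1.2) are not shown. A closed-book instruction there cannot be excluded. This stands: the point is that the protocol text describes no such control, not that none exists.

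**Any self-administered online survey allows look-up, and related limits are reported.** The first part is true. The second helps little: source of knowledge and having read the Guide are summarised, but neither identifies answers looked up during the survey.

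**The size is unknown.** This stands. Moderate changes in the assumed rates remove the reversal, as the 78.4% and 79.5% rows show.

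**Reading the Guide is what the measure intends.** This stands for re-reading beforehand. HCPs who re-read the Guide because of the survey should not be taken out of any analysis; it is enough to name the possibility as a limitation. Consulting it while answering is different, because the item is scored as understanding.

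**Stronger readings that the text does not support.** A reader might infer that liaisons coach HCPs on the risks. The protocol says only that they discuss the study, stress its importance and encourage participation, which supports advance notice and no more. A reader might also take Objective 1 to mean understanding as carried into routine counselling. Section 8 does not say that.

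**Conclusion.** The point holds as a gap in the plan's bias control and stated limitations. In-person promotion, unsupervised completion and provision of the Guide at the centres are all in the text. No listed control, limitation, variable or analysis deals with consulting the Guide while answering, and the 80% rule rests on a point estimate that look-up would be expected to inflate.

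The size of the bias cannot be derived from the documents. A reader might infer from the 81.9% example that a failing KRM would become a success. That rests wholly on assumed rates, and under equally plausible ones the KRM still fails. The supported conclusion is that the correct rate may be biased upward and that the planned data could not show whether it was. This is an inexpensive improvement worth making before the questionnaire is final; it does not invalidate the design.

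**What to change.** 1. **Sections 9.4 and 9.9.1.** State that the opening screen asks respondents to answer without consulting the Guide, product information or colleagues. If Appendix 1.1 already has this instruction, cite it.
2. **Questionnaire and section 9.7.4.** After the last knowledge question, add one item on whether any material was consulted while answering. Report each KRM rate also without those respondents, as a descriptive sensitivity row.
3. **Section 9.9.** List look-up during the survey, and re-reading of the Guide prompted by it, as limitations.

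No restriction on supplying the Guide is needed or advisable. It is a risk-minimisation tool distributed under plans agreed with national authorities, and holding it back from invited HCPs could last for the whole data collection window.

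**Cost.** One instruction, one item, one row per KRM and a sentence. Section 9.4 places user testing before the questionnaire is finalised, so the additions can be tested with the rest. The closing item is itself self-reported. The sensitivity row rests on fewer respondents: if 9 of 30 are removed, 21 remain, and 17/21 (81.0%) has an exact 95% interval of 58.1% to 94.6%, against 61.4% to 92.3% for 24/30. The reported rates may also be slightly less favourable.

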#### 9.9.1 Controls to Minimize Bias

A number of controls will be in place to ensure that the survey is conducted to minimize bias, including the following:

- Knowledge questions will be randomized and presented individually to minimize the potential for positional bias.
- HCPs cannot skip ahead or go back to a question once the question has been answered. All questions presented must be answered in order to complete the survey.
- HCPs will be provided with a unique code during the recruitment process in order to gain access to the internet-based systems. The code will be inactivated after use to minimize exposure bias and fraud.
- Respondent identifiers will be stored separately from survey responses thus limiting HCP concerned that their answers will be identified. This is likely to minimize the social desirability bias and improve response rates.

### 9.10 Other Aspects

Not Applicable

### 10 PROTECTION OF HUMAN SUBJECTS

#### 10.1 Personal Information and Consent

All data collected during the survey will be kept confidential and used only for the purposes stated in the survey instructions. The collection of any personal, identifying information (first name, last name, address) from respondents will only be used for the processing of the HCPs' financial compensation and to comply with laws and regulations regarding notification of payments made on behalf of a pharmaceutical company. Respondent identifiers will be stored in a separate encrypted electronic database from the survey responses. The EDC system used for data collection of the survey responses does include any identifiable information.

By answering the first question of the survey ("Do you agree to participate in this survey?"), respondents are providing informed consent for participation in the research study.

## 10.2 Respondent Withdrawal

Respondents can decline to participate or stop taking the survey at any time.

#### 10.3 Ethics Committee

Approval of this protocol by the respective local Ethics Committee will be obtained prior to initiating the survey in each country, where applicable.

### 10.4 Ethical Conduct of the Study

The study will be conducted in accordance with legal and regulatory requirements, as well as with scientific purpose, value and rigor, and follow generally accepted research practices described in:

- Guideline on Good Pharmacovigilance Practices (GVP) Module XVI Risk Minimisation Measures: Selection of Tools and Effectiveness Indicators,
- Guidance for Good Pharmacoepidemiological Practice issued by the International Society of Pharmacoepidemiology (ISPE),
- International Ethical Guidelines for Epidemiological Research issued by the Council for International Organizations of Medical Sciences (CIOMS), and
- Guide on Methodological Standards in Pharmacoepidemiology issued by the EMA European Network of Centres for Pharmacoepidemiology and Pharmacovigilance (ENCePP).

# 11 MANAGEMENT AND REPORTING OF ADVERSE EVENTS / ADVERSE REACTIONS

Adverse events will not be actively collected as this study is assessing HCPs' understanding of the important safety information detailed in the Guide for HCPs and the distribution of the Patient/Carer Guide and Patient Card to patients being treated with Casgevy.

# 12 PLANS FOR DISSEMINATING AND COMMUNICATING STUDY RESULTS

The final report will be submitted to the EMA and other regulatory agencies as applicable. The study, including the final report, will also be registered in the Heads of Medicines Agencies - EMA Catalogues of real-world data sources and studies. The study findings may be submitted to a scientific congress and/or to a peer-reviewed journal.

## **ANNEX 1. LIST OF STAND-ALONE DOCUMENTS**

Number	Document Reference Number	Title
1	Appendix 1.1	Healthcare Professional Survey
2	Appendix 1.2	Sample Draft Survey Invitation Letter for Healthcare Professional
3	Appendix 1.3	Guide for HCPs, Guide for Patients/Carers and Patient Card
